## **9 SENSITIVITY ANALYSES**

The following sensitivity analyses are planned:

- 1) Apneic events that cannot be adjudicated will be counted as non-apneic events, and the PO-1 and SO-2 (severe cardiorespiratory events) will be reanalyzed.
- 2) All apneic events determined by the cardiorespiratory monitor will be counted as apneic events, regardless of manual review, and the PO-1 and SO-2 (severe cardiorespiratory events) will be reanalyzed.
- 3) The following infants will be excluded from analysis and all objectives re-analyzed:
  - a. Infants with a major surgical procedure (including circumcision) during the study period.
  - b. Receipt of any intramuscular injection, including Synagis or a vaccine other than DTaP, IPV, HBV, PCV13, or Hib during the study period.

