5.5.3 Vaccine Supply, Storage, and Administration	22
6 STATISTICAL CONSIDERATIONS	22
6.5 SAMPLE SIZE AND POWER ESTIMATION	23
6.6 ANALYSIS PLAN.....	23
6.6.1 Pilot Study	23
6.6.2 Full Study	23
6.7 DATA MANAGEMENT	26
6.7.1 Research Electronic Data Capture (REDCap)	27
6.8 ROLE OF THE CDC INVESTIGATORS IN THE PROJECT	27
7 HUMAN SUBJECTS	28
7.5 HUMAN SUBJECTS INVOLVEMENT, CHARACTERISTICS, AND DESIGN.....	28
7.6 SOURCES OF MATERIAL.....	28
7.7 POTENTIAL RISKS AND BENEFITS	28
7.8 ADEQUACY OF PROTECTION AGAINST RISKS	29
7.8.1 Protections against Risk	29
7.8.2 CLINICALTRIALS.GOV REQUIREMENTS.....	29
7.9 HUMAN SUBJECTS.....	29
7.9.1 Vulnerable Subjects Research	29
REFERENCES	30

PROTOCOL SUMMARY

Title:	A Prospective, Randomized, Open-label Clinical Trial to Assess Apnea Following Administration of 13-valent Conjugate Pneumococcal Vaccine, Diphtheria Toxoid, Tetanus Toxoid, and Acellular Pertussis Vaccine, Inactivated Polio Vaccine, Hepatitis B Vaccine, and Haemophilus influenzae Type B Vaccine in Preterm Infants
Phase:	Phase 4
Population:	Up to 300 premature infants <33 weeks and 0 days gestational age and 6-12 weeks postnatal age who will receive 13-valent Conjugate Pneumococcal Vaccine (PCV13), Diphtheria Toxoid, Tetanus Toxoid, and Acellular Pertussis Vaccine (DTaP), Hepatitis B vaccine (HBV), and Haemophilus influenzae Type B Vaccine (Hib)
Clinical Sites:	Three: Duke University (Lead); University of North Carolina (Lead Subcontractor); Cincinnati Children’s (Contributing)
Study Duration:	28 months
Participant Duration:	Up to 14 days
Description of Study Procedures:	This is a prospective, randomized, open-label clinical trial. Infants will be randomized (1:1) to receive either simultaneous administration of PCV13, DTaP, HBV, IPV, and Hib vaccines or no vaccination. Unvaccinated infants will be followed for 48 hours after randomization to capture episodes of apnea. Vaccinated infants will be followed for 48 hours after vaccination for apnea. In addition, vaccinated infants will be followed for 14 days after vaccination for adverse events using information documented in the medical record or obtained by phone call to the parent/legally authorized representative (LAR) on day 14.

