- Record standard of care procedures (including, but not limited to, any surgical procedures, eye exams, central line placements)
- Record clinically important adverse events (including apnea) and serious adverse events
- Of note, the unvaccinated group completes the study 48 hours after randomization.

Study Days 3-14 (Vaccinated group only)

**This period of time (day 3-14) will begin at 48 hours after vaccination.*

- Record clinically important adverse events (including apnea) and serious adverse events in vaccinated group only
 - If infant is discharged from the hospital prior to day 14, then follow-up of events will occur via telephone call with the parent/LAR and/or chart review of outpatient clinic notes or inpatient clinic notes (if infant is rehospitalized and these are available).

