All participants will have data captured from their continuous cardiorespiratory and pulse oximetry monitoring after randomization. Capture of continuous monitoring data will begin at randomization and end at 48 hours after vaccination (vaccinated group) or randomization (unvaccinated group). If infants in the vaccinated group are not vaccinated by 12 hours after randomization, capture of monitoring data will end at 60 hours after randomization. At the end of the 48-hour monitoring period, study staff at all enrolling sites will collect digital or printed output of data from cardiorespiratory monitors for all infants and send to the analysts at Duke University who will be blinded to the randomization group of the participants. To ensure the analysts are blinded to the treatment arms, the data obtained from the monitor for each infant will not include any personal or study identifiable information. Each output will be assigned a non-sequential coded number before they are sent to the analysts. The blinded analysis will interpret the output and record the date, time, and duration of each cardiorespiratory event (apnea, bradycardia, desaturation, and severe cardiorespiratory event) as defined below.

Procedures

[figure not shown]
Any procedures done as part of routine care (including, but not limited to, surgical procedures, eye exams, and central line placements) that occur beginning at randomization and ending at 48 hours after vaccination (vaccinated group) or randomization (unvaccinated group) will be recorded. Procedures occurring >60 hours after randomization in the vaccinated group will not be recorded. Data recorded will include the type of procedure, date/time of the procedure, length of the procedure, and a narrative describing any other important clinical information regarding the procedure.

Clinically important adverse events: days 1-2

Clinically important adverse events will be collected from randomization to 48 hours following randomization (unvaccinated group) or vaccination (vaccinated group). The following clinically important adverse events will be collected:

1. Apnea (*POM 1.1, SOM 1.1, SOM 1.2*)

- a. *Definition:* Apnea will be defined as a pause in respirations of >20 seconds, or a pause in respirations of >15 seconds with associated bradycardia (heart rate <80 beats per minute).
 - b. *Method of collection:* Obtained from the cardiorespiratory monitor as described above.
2. Increase in mode of respiratory support (SOM 1.3)

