5.5 Follow-up on days 3-14 for infants in the vaccinated group

**This period of time (day 3-14) will begin at 48 hours after vaccination.*

Infants in the vaccinated group will be followed for the above clinically important AEs, SAEs, and concomitant medications on days 3-14. If an infant in the vaccinated group is discharged or transferred prior to day 14 (with no EHR accessible), then these data will be obtained via follow-up phone call from the study staff to the parent/guardian.

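### SAP Section 9 item 3b excludes infants for any intramuscular injection and reruns all objectives, so it removes cases of EOM 2.3; the item's time window is also undefined

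*SAP*

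**What the plan says.** SAP Section 9, item 3, opens with "The following infants will be excluded from analysis and all objectives re-analyzed". Item 3a names "Infants with a major surgical procedure (including circumcision) during the study period"; item 3b names "Receipt of any intramuscular injection, including Synagis or a vaccine other than DTaP, IPV, HBV, PCV13, or Hib during the study period". The only intramuscular products spared are the study antigens.

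EOM 2.3 (SAP 3.3 and 8.3b) counts infants with a blood culture, or with intravenous or intramuscular antibiotics given alongside one, in the 48-hour window. EOM 3.3 (SAP 3.3 and 8.3c) counts the same events from 48 hours to 14 days in vaccinated infants. Protocol 5.4 collects new antibiotics by either route for both measures.

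Neither document defines *study period*. Follow-up differs by arm. According to the Protocol Summary, "vaccinated infants will be followed for 14 days after vaccination for adverse events", while Protocol 5.2 notes that "the unvaccinated group completes the study 48 hours after randomization".

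**The concern.** A sensitivity analysis that excludes infants should do so on grounds that are not part of the outcome being rerun. Item 3b does not meet that test for EOM 2.3. An infant given intramuscular antibiotics for a sepsis evaluation in the outcome window is a case by definition, and the rule removes that infant from the rerun in which it should count.

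The effect may reach further. The trial compares sepsis evaluation and treatment between arms under EO-2, so the plan itself does not assume the arms are equal on it. If the frequency of this treatment, or the apnea risk of the infants who receive it, differs by arm, dropping them from the PO-1, SO-1, SO-2 and EO-1 reruns conditions on a post-randomization outcome.

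The undefined window adds a second difficulty: two programmers could build different exclusion lists from the same text.

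**Working it through.** **The plan's own figure.** With 135 per group, 15% versus 30%, and two-sided alpha 0.05, the pooled proportion is 0.225. The null standard error is √(2 × 0.225 × 0.775 / 135) = 0.0508, and the alternative standard error is √((0.15 × 0.85 + 0.30 × 0.70) / 135) = 0.0500. Power = Φ((0.15 − 1.96 × 0.0508) / 0.0500) = 84.3%, as stated, and 270 / 0.9 = 300. Nothing below changes these figures.

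**Effect on EOM 2.3.** Let q be the true risk in an arm and s the share of cases given intramuscular antibiotics. Assume no other exclusions. Removing the fraction qs leaves q(1 − s) cases and 1 − q non-cases, so

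- remaining risk = q(1 − s) / (1 − qs)
- remaining odds = (1 − s) × q / (1 − q)

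The documents give neither q nor s. With assumed risks of 10% (vaccinated) and 5% (unvaccinated), and the same s in both arms:

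| s | vaccinated | unvaccinated | difference (points) | odds ratio |
|---|---|---|---|---|
| 0 | 10.0% | 5.0% | 5.0 | 2.11 |
| 10% | 9.1% | 4.5% | 4.6 | 2.11 |
| 25% | 7.7% | 3.8% | 3.9 | 2.11 |
| 50% | 5.3% | 2.6% | 2.7 | 2.11 |

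If s differs by arm, the odds ratio is multiplied by (1 − s_vaccinated) / (1 − s_unvaccinated). With 25% and 10% the factor is 0.75 / 0.90 = 0.83, and 2.11 becomes 1.76. With the shares reversed it is 0.90 / 0.75 = 1.20, and 2.11 becomes 2.53.

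**Effect on the other 48-hour outcomes.** If a fraction f of an arm with risk p is removed and those infants have risk a, the remaining risk is (p − fa) / (1 − f). This is above p when a < p and below p when a > p. The documents give neither f nor a, so the direction is open.

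**What *study period* means.**

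- *For the short window.* Protocol 5.4, defining increased respiratory support in later follow-up, places the end of the study period on day 3. SAP 7.1 groups Synagis with procedures, and Protocol 5.4 stops recording procedures at 48 hours after vaccination or randomization; "Procedures occurring >60 hours after randomization in the vaccinated group will not be recorded". SAP 6.3 excludes unvaccinated infants vaccinated in the study period, and Appendix 1 item 4 turns this into 48 hours. That last pair is weaker evidence, since a control's participation ends at 48 hours on either reading. Exclusion criteria 2 and 13 (Protocol 4.2), which item 3 resembles, look ahead 60 hours from randomization.
- *For the long window.* Protocol 5.5 says "Infants in the vaccinated group will be followed for the above clinically important AEs, SAEs, and concomitant medications on days 3-14", and Protocol 5.4 uses the same term for collecting caffeine and acetaminophen.

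For scale, assume 150 infants per arm and a constant rate r of qualifying events per 48 hours, which the documents do not give. Vaccinated exclusions are 150 × (1 − (1 − r)^(hours / 48)), and control exclusions are 150r:

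| r | controls, 48 h | vaccinated, 60 h | vaccinated, 14 days |
|---|---|---|---|
| 1% | 1.5 | 1.9 | 10.2 |
| 2% | 3.0 | 3.7 | 19.8 |
| 5% | 7.5 | 9.3 | 45.2 |

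**EOM 3.3.** Its events fall after 48 hours. Item 3b deletes them for certain only on the long reading; the loss of EOM 2.3 cases occurs on either reading.

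**The case against.** The strongest reply is that this is a minor feature of one sensitivity analysis. EOM 2.3 is exploratory, it also counts blood cultures without antibiotics, its main mITT analysis keeps every infant, and its odds ratio does not move if the intramuscular share is equal in both arms. All of that stands, and it limits the severity. It does not make the exclusion sensible, because equality of the share cannot be taken for granted.

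A second reply is that item 3b exists to remove infants exposed to another injection, and that exempting antibiotics leaves some of them in the PO-1 rerun. This is a fair cost, to be weighed against selecting on an adverse outcome.

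A reader might infer something stronger: that item 3 excludes over 14 days in vaccinated infants and 48 hours in controls, so the rerun is biased towards a vaccine effect. The documents do not support stating this as fact. For item 3a the later procedure data are not collected. For injections, the term is undefined and most of its uses point to the short window. The only injections expressly collected after 48 hours are antibiotics started with a blood culture, and the named on-study medications are caffeine and acetaminophen. No removal fraction can be derived, and the direction reverses according to whether the removed infants have lower or higher apnea risk than the rest.

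**Conclusion.** The point holds at low severity. On the text, item 3b removes EOM 2.3 cases from the EOM 2.3 rerun, and it can select on outcome in the other 48-hour comparisons. The undefined window is a drafting gap: a 14-day reading in the vaccinated arm alone is possible, but the documents favour the short one, on which the arms differ by at most 12 hours (60 / 48 = 1.25).

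The size and direction of any bias cannot be derived from the documents. The tables above rest on assumed risks, shares and event rates and show only how the rule behaves. The primary mITT analysis, the 84.3% power and the total of 300 infants are unaffected.

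**What to change.** Amend SAP Section 9, item 3, before it is run:

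- State that infants are not excluded under item 3b solely for intramuscular antibiotics started with a blood culture. At minimum, omit EOM 2.3 and EOM 3.3 from this re-analysis. The minimum version protects those two measures but leaves possible selection on outcome in the other 48-hour comparisons.
- Replace *during the study period* in items 3a and 3b with a window from randomization to the end of the infant's 48-hour mITT outcome window, at most 60 hours after randomization. Starting at randomization covers events before vaccination. State that the same window defines the exclusions for the EO-3 rerun.

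The cost is a few sentences and no new data collection. A few infants with a non-vaccine injection stay in the rerun, and the vaccinated arm keeps a window up to 12 hours longer than the control arm, which the SAP should acknowledge.

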## **10 INTERIM SAFETY DATA REVIEW**

Given that this study involves administering U.S.-licensed vaccines recommended by the ACIP for preterm infants and included as part of routine clinical care, there will not be a designated data safety monitoring board for this study. However, due to the fragility of the study population and interventional design, one interim safety data review will be performed with the goal of identifying unexpected safety concerns of clinical importance. The safety data review will provide the study the opportunity to identify unexpected safety concerns and make changes to the protocol if needed. The interim safety data review will be done by a safety monitoring panel with relevant expertise, comprised of experts who are not co-investigators on this study. The safety population for the interim safety review will include infants who were enrolled and randomized. Infants who participated in the pilot study will also be included. The safety monitoring panel will review clinical narratives of SAEs. If the CDC and study investigators determine additional analyses or reviews are needed, efforts will be made to conduct additional analysis or reviews that will not include analyzing the primary endpoint as a first step. This is to avoid introducing bias or increasing sample size needs for statistical power.

## Appendix 1

### Major Protocol Violations for Analysis

1. Infant later found to have not met inclusion/exclusion criteria at the time of study entry.
  - a. Infant will not be counted as a protocol violation for analysis if the only exclusion criterion met is that the child or parent/LAR is an immediate relative of study staff or an employee who is supervised by study staff.
2. Infant did not have cardiorespiratory monitoring data for the fully specified time period after vaccination/randomization
  - a. Vaccinated group: No cardiopulmonary data for 48 or more hours after vaccination. Infants with <1 hour of absent cardiopulmonary data for this period will not be considered a violation for analysis.
  - b. Unvaccinated group: No cardiopulmonary data for 48 or more hours after randomization. Infants with <1 hour of absent cardiopulmonary data for this period will not be considered a violation for analysis.
3. Infant did not receive all vaccines by 12 hours after randomization in the vaccinated group
4. Infant in the unvaccinated group received vaccines during the 48 hours after randomization.

